The change in the gastric emptying rate AUC from baseline to Day 28 will be analyzed in the FAS using an analysis of covariance (ANCOVA) model with treatment group (three levels) and types (IG, DG) as a factor and the baseline GEBT as a covariate. Each of the two primary comparisons (0.1 mg versus placebo, 0.5 mg versus placebo) will be conducted using a two-sided Dunnett's test at the overall alpha=0.05 significance level.

Other efficacy analyses:

All secondary endpoints will be analyzed using the same types of ANCOVA models as described for the primary analysis. Each treated group will be compared to placebo. All secondary analyses will be conducted with no adjustment for multiplicity.

Subgroup analysis:

A subgroup analysis of idiopathic gastroparesis patients compared to diabetic gastroparesis patients will be performed for all efficacy analysis endpoints.

Pharmacokinetic Assessment

Plasma concentrations will be used to estimate the pharmacokinetic parameters for PCS12852 on Day 1 and Day 28 using noncompartmental methods in WinNonlin[®]. The following parameters will be calculated as data permit:

- C_{max}: maximum observed plasma concentration
- T_{max}: time at which the maximum plasma concentration was observed
- $t_{1/2}$: (the apparent first-order terminal elimination half-life)

Version 3.0 14 of 85 20 April 2022

Name of Investigational Product: PCS12852

Name of Active Ingredient: PCS12852

- AUC_{0-last}: the area under the plasma concentration versus time curve, from time 0 to the last measurable concentration
- AUC $_{\infty}$: the area under the plasma concentration vs. time curve from time 0 to infinity
- λ_z : apparent first order terminal elimination rate constant

A dose proportionality analysis will be conducted for log-transformed C_{max} , AUC_{0-last} , and AUC_{∞} using the power model. In addition, the relationship between gastric emptying rate and drug exposure will be assessed, as data permit. Exposure-response for safety measures may also be explored. Details of these analysis will be provided in the Statistical Analysis Plan.

In addition, a population PK model may be used to describe the PK of PCS12852, if appropriate based on the data collected. A previously developed population PK model describing the PK of PCS12852 in patients with functional constipation, using a two-compartment model with first order absorption, may be used to predict the PK in patients in this study.

Safety Analyses:

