9.2 Statistical Analyses

9.2.1 General Considerations

Approximately 24 patients (approximately 8 patients in each of the three treatment groups) with moderate to severe gastroparesis who have documented delayed gastric emptying are planned to be randomized (1:1:1) in the study. The randomization to treatment groups will be stratified by type of gastroparesis (idiopathic, diabetic), enrolling at least 2 patients of each type of gastroparesis (idiopathic, diabetic) in each treatment group.

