9.2.2 Primary Efficacy Analysis

The change in the gastric emptying rate AUC as measured by the GEBT, from baseline to Day 28 will be analyzed in the FAS using an analysis of covariance (ANCOVA) model with treatment group (three levels) as a factor and the baseline GEBT as a covariate. Each of the two primary comparisons (0.1 mg versus placebo, 0.5 mg versus placebo), will be conducted using a two-sided Dunnett's test at the overall alpha=0.05 significance level.

Other efficacy analyses:

Version 3.0 55 of 85 20 April 2022

All secondary endpoints will be conducted using the same approach as described for the primary analysis. Each treated group will be compared to placebo using Dunnett's test. All secondary analyses will be based on the use of two-sided tests at the alpha=0.05 overall level of significance, with no adjustment for multiplicity.

Subgroup analysis:

A subgroup analysis of idiopathic gastroparesis patients compared to diabetic gastroparesis patients will be done for all efficacy analysis endpoints.

Pharmacokinetic analysis:

Plasma concentrations will be used to estimate the pharmacokinetic parameters for PCS12852 on Day 1 and Day 28 using noncompartmental methods in WinNonlin®. The following parameters will be calculated as data permits:

- C_{max}: maximum observed plasma concentration
- T_{max} : time at which the maximum plasma concentration was observed
- t_{1/2}: (the apparent first-order terminal elimination half-life)
- AUC_{0-last}: the area under the plasma concentration versus time curve, from time 0 to the last measurable concentration
- AUC $_{\infty}$: the area under the plasma concentration vs. time curve from time 0 to infinity
- λ_z : apparent first order terminal elimination rate constant

A dose proportionality analysis will be conducted for log-transformed Cmax, AUC0-last, and $AUC\infty$ using the power model. In addition, the relationship between gastric emptying rate and drug exposure will be assessed, as data permit. Exposure-response for safety measures may also be explored.

In addition, a population PK model may be used to describe the PK of PCS12852, if appropriate based on the data collected. A previously developed population PK model describing the PK of PCS12852 in patients with functional constipation, using a two-compartment model with first order absorption, may be used to predict the PK in patients in this study.

Further details of all analyses will be described in the SAP.

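### The IG-versus-DG subgroup analysis covers every efficacy endpoint, with as few as 2 patients per type per arm and no treatment-by-type model to make the comparison

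*Combined protocol and SAP*

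**What the plan says.** Section 9.2.2, under subgroup analysis, says: "A subgroup analysis of idiopathic gastroparesis patients compared to diabetic gastroparesis patients will be done for all efficacy analysis endpoints". The synopsis makes the same commitment: "A subgroup analysis of idiopathic gastroparesis patients compared to diabetic gastroparesis patients will be performed for all efficacy analysis endpoints".

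Section 9.2.1 plans "Approximately 24 patients (approximately 8 patients in each of the three treatment groups") and stratifies randomization by type, "enrolling at least 2 patients of each type of gastroparesis (idiopathic, diabetic) in each treatment group".

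The primary ANCOVA is stated in two forms. Section 9.2.2 has a "model with treatment group (three levels) as a factor and the baseline GEBT as a covariate". The synopsis has a "model with treatment group (three levels) and types (IG, DG) as a factor and the baseline GEBT as a covariate". The first leaves out type. The second includes it as a main effect only. Neither has a treatment-by-type term.

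The primary dose-placebo comparisons use Dunnett's test "at the overall alpha=0.05 significance level". Section 9.2.2 also applies Dunnett's test to each secondary endpoint, but across secondary endpoints it proceeds "with no adjustment for multiplicity". No model, alpha, minimum size or descriptive label is given for the subgroup analysis. Further detail is left to a SAP, and the supplied text contains no separate SAP.

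**The concern.** The plan wants to compare the two types, but no stated model estimates whether the drug effect differs between them. The easiest way to carry out the sentence is to rerun the ANCOVA within each type and see which type reaches significance. With groups this small, that comparison mostly reflects chance and the unequal sizes of the two types.

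Section 2.2 raises possible differences between diabetic and idiopathic patients, so readers will look for one. A significant result in one type beside a non-significant result in the other could be taken as a real difference and could steer the population of the next trial.

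**Working it through.** **Inputs.** 24 patients, about 8 per arm, and at least 2 of each type per arm (Section 9.2.1). SD 15, difference 25, two-sided alpha 0.025, 80% power, and SD estimates of 10 to 35 from Study 102 (Section 9.3). ANCOVA with treatment and baseline (Section 9.2.2).

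**The plan's own figure.** Noncentral-t power with 8 per arm, difference 25, SD 15 and alpha 0.025 is 78.4% with 14 df (two arms) and 81.0% with 20 df (three-arm ANCOVA). The stated 80% is reproduced.

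**Error df.**
- Separate model within a type: intercept, 2 treatment terms and baseline are 4 parameters. With n per arm in that type, df = 3n − 4, which is 2, 5 and 8 for n = 2, 3 and 4.
- Pooled model: intercept, 2 treatment, 1 type, 2 interaction and 1 baseline term are 7 parameters, so df = 24 − 7 = 17.

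**Precision of a dose-placebo difference within a type.** Half-width = t(0.975, df) × SD × √(2/n), with unadjusted t. Baseline imbalance is ignored, so these are best cases. At SD 15:

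| n per arm in the type | SE | Separate model | Pooled model (t = 2.110) |
|---|---|---|---|
| 2 | 15.0 | 4.303 × 15.0 = 64.5 | 31.6 |
| 3 | 12.25 | 2.571 × 12.25 = 31.5 | 25.8 |
| 4 | 10.61 | 2.306 × 10.61 = 24.5 | 22.4 |

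At 2 per arm, over SD 10 to 35, the half-width is 43 to 151 for the separate model and 21 to 74 for the pooled model.

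**Discordant significance when the types do not differ.** True effect 25 in both types, SD 15, separate models, two-sided 0.05 unadjusted. Power is 17% at 2 per arm, 54.4% at 4 per arm and 77% at 6 per arm. The two types are independent, so for one dose:
- 4/4 split: 2 × 0.544 × 0.456 = 0.50.
- 2/6 split: 0.17 × 0.23 + 0.77 × 0.83 = 0.68.

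With Dunnett critical values, power is 42.6% at 4 per arm, and 11.4% and 66.8% at 2 and 6 per arm. Discordance is then 2 × 0.426 × 0.574 = 0.49 at 4/4, and 0.114 × 0.332 + 0.668 × 0.886 = 0.63 at 2/6.

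**Number of tests.** The primary and secondary efficacy endpoints are AUC, t10, t50 and four weekly ANMS GCSI-DD changes, which makes 7. With Dunnett covering both doses within each endpoint and type, there are 7 × 2 = 14 families. With no drug effect, the chance of at least one false positive is 1 − 0.95^14 = 0.51 if the families are independent, and lower with positive correlation.

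**Type I error at low df.** Simulating the within-type ANCOVA at 2 per arm with no effect gave rejection in 5.1% of comparisons, so the nominal level holds.

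**The IG-DG difference in effect, pooled model.** Half-width = 2.110 × SD × √(2/a + 2/b), where a and b are the numbers per arm in the two types. At SD 15 this is 31.6 at 4/4 and 36.5 at 2/6.

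**The case against.** The strongest reply is that separate within-type ANCOVAs appear nowhere in the plan. A comparison of one type with the other could equally mean an interaction contrast, and the detail is deferred to the SAP. That stands: the 2 df and the 64.5 belong to one reading. They also belong to the permitted floor. If types were enrolled in the 36:29 idiopathic-to-diabetic ratio of the series cited in Section 2 (an assumption), a type would have 6 or fewer of 24 patients only about 4% of the time. At 4 per arm the gain from pooling is small, 24.5 against 22.4.

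Three stronger readings are tempting and are not supported.
- A reader might count each dose separately, giving 7 × 2 × 2 = 28 tests and 1 − 0.95^28 = 0.76. Section 9.2.2 applies Dunnett across doses, so 14 families and about 51% is the fairer figure. Even that is high, because AUC, t10 and t50 come from one breath curve and the diary endpoints are successive weeks in the same patients.
- A reader might infer that 2 error df produces excess false positives. It does not, as the 5.1% shows.
- A reader might infer that the primary analysis is compromised. It is not. The subgroup results support no listed objective and carry no power claim.

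The reply does not remove the main point. The protocol already fixes the scope at all efficacy endpoints, and the discordance of about one half arises at an even split, not only at the floor.

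**Conclusion.** The point holds as a weakness in how the subgroup analysis is framed, and it is worth correcting before the SAP is final. The plan commits to comparing the types on every efficacy endpoint without the one term that makes the comparison. This leaves room to judge each type by its own p-value.

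Run that way, a given dose would be significant in one type and not the other about 50% of the time at 4/4 and 68% at 2/6, although the drug works equally in both. These figures rest on SD 15, a true effect of 25, complete data and separate models. The penalty in precision is large at 2 per arm (64.5 against 31.6), moderate at 3 (31.5 against 25.8) and small at 4 (24.5 against 22.4). The damage comes from imprecision, unequal power between types and the number of tests.

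**What to change.** 1. Include type as a main effect in the primary ANCOVA on all randomized patients, so that Section 9.2.2 agrees with the synopsis.
2. For the subgroup analysis of the primary AUC, add treatment-by-type to that model. Report the dose-placebo difference within each type, and the IG-DG difference in effect, with 95% confidence intervals from the pooled error variance. State that types will not be judged by separate within-type p-values.
3. State that by-type results for all other efficacy endpoints are descriptive.

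This is a change of protocol and SAP wording. It needs no new patients or data and reduces the analysis work. It assumes equal error variance in IG and DG, which the main ANCOVA already assumes. It does not make the type comparison informative: at SD 15 the half-width of the IG-DG contrast is still 31.6 to 36.5, wider than the planned effect of 25, and the report should say so.

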9.2.3 Secondary Efficacy Analysis

This study will enroll gastroparesis patients with documented delayed gastric emptying and at least moderate symptom severity. The ANMS GCSI-DD scale will be used to assess the change from baseline in symptoms.

The ANMS GCSI-DD symptom assessments are based on a 24-hour recall period to minimize bias in patient recall. The ANMS GCSI-DD total gastroparesis symptom daily score is generated by summing the scores on each of the five symptom items (nausea, early satiety, postprandial fullness, upper abdominal pain, and number of vomiting episodes) and then dividing by 5, that is the number of items within the gastroparesis related symptom score. Thus, the maximum total symptom score could be (5 symptoms x maximum score 4 divided by 5); hence, the maximum score is 20/5=4. The ANMS GCSI-DD gastroparesis symptom daily score can range from 0 to 4. High scores on the ANMS GCSI-DD reflect greater symptom severity.

9.2.4 Other Patient-reported outcomes (PRO) Assessments – Exploratory Endpoints

The PAGI-SYM is a patient-reported outcome that asks patients the severity of their symptoms over the last 2 weeks. The PAGI-SYM was developed to measure symptom severity for gastroparesis, functional dyspepsia, and gastroesophageal reflux disease. The PAGI-SYM is composed of 20 items and 6 subscales: heartburn/regurgitation (7 items), nausea/vomiting (3 items), postprandial fullness/early satiety (4 items), bloating (2 items), upper abdominal pain (2 items), and lower abdominal pain (2 items). Subscale scores are calculated by averaging across items comprising the subscale; scores vary from 0 (none or absent) to 5 (very severe). The half-scale rule is applied for missing data (i.e., the subscale score is calculated by using the mean of non-missing items; when more than 50% of items are missing, the score is set to missing). The change from baseline in the PAGI-SYM will be analyzed using the same statistical approach as described for other analyses.

The PGI-C is a patient-reported questionnaire with a 7-point rating scale where the participant rates his/her own improvement in overall symptoms relative to the baseline assessment. It is rated as 1, very much improved; 2, much improved; 3, minimally improved; 4, no change; 5, minimally worse; 6, much worse; or 7, very much worse.

The PGI-S is a patient reported questionnaire with a single question to measure disease severity on a 5-point rating scale. It is rated as "none," "mild," "moderate," "severe," and "very severe."

Version 3.0 57 of 85 20 April 2022

The PAGI-QOL is a 30-item instrument assessing quality of life in patients with gastroparesis. The questionnaire covers 5 domains: Daily Activities, Clothing, Diet and Food Habits, Relationship, and Psychological Well-Being and Distress. The effect on overall quality of life and well-being over the past 2 weeks is rated on a scale of 0 (none of the time) to 5 (all of the time) for each item.

Clinicians complete the CGI-S, which is a 7-point scale on which the clinician rates the severity of the patient's gastroparesis at the time of assessment and refers to the degree of illness at the time of the visit and during the 2 weeks before the visit. The CGI-S is rated on the following 7-point scale: 1: normal, not at all ill; 2: borderline ill; 3: mildly ill; 4: moderately ill; 5: markedly ill; 6: severely ill; 7: among the most extremely ill patients.

The CGI-I is a 7-point scale in which the clinician rates the change from the initiation of treatment. The CGI-I is rated as: 1: very much improved since the initiation of study treatment; 2: much improved; 3: minimally improved; 4: no change from baseline (the initiation of study treatment); 5: minimally worse; 6: much worse; and 7: very much worse since the initiation of study treatment.

9.2.5 Safety Analyses

The safety analyses will be performed using the Safety Population and include AEs, changes in physical exam findings, vital signs, ECGs and clinical laboratory values.

Adverse events will be coded using the current version of the Medical Dictionary for Regulatory Activities (MedDRA version 23.0 or higher). The number and percent of patients reporting at least one AE will be summarized by System Organ Class and Preferred Term and presented by severity, relationship to study treatment, amount of drug exposure, and time. Each patient will contribute only once (i.e., first occurrence) to each of the incidence rates, regardless of the number of occurrences. Severity of AEs will be assessed based on the National Cancer Institute (NCI) CTCAE Version 5.0. For reporting of AE severity in patients with more than one occurrence of the same AE, the patient will only be reported once based on the highest severity of the AE observed. Patients who have an SAE or who discontinue the study due to an AE deemed to be related to study treatment will be described in patient narratives.

Vital signs, clinical laboratory, and ECG results will also be presented and summarized by dose level and summarized by descriptive statistics with change from baseline values calculated. All safety data collected in the clinical database, including physical exam findings and abnormal ECG results, will be presented in data listings. The safety categories will be summarized as appropriate (eg, categorial or continuous descriptives, shift tables) and will be fully defined in

Version 3.0 58 of 85 20 April 2022

the SAP. The potential relationship between abnormal ECG results and PK will also be evaluated and fully defined in the SAP.

9.3 Sample Size Determination

Based on the results of a prior study (Study 102), estimates of the standard deviation (SD) of the AUC change from baseline range from 10 to 35. Assuming a true SD of 15 and based on a two-sided test at the alpha=0.025 level of significance, a sample size of 8 patients per arm (24 total patients) will provide 80% power to detect a between-group mean difference of 25.

Version 3.0 59 of 85 20 April 2022

10 Supporting Documentation and Operational Considerations

10.1 Appendix 1: Regulatory, Ethical, and Study Oversight Considerations

10.1.1 Regulatory and Ethical Considerations

This study will be conducted in accordance with the protocol and with:

- Consensus ethical principles derived from international guidelines including the Declaration
 of Helsinki and Council for International Organizations of Medical Sciences international
 ethical guidelines.
- Applicable ICH Good Clinical Practice (GCP) guidelines.
- Applicable laws and regulations.

The protocol, protocol amendments, ICF, Investigator's Brochure, and other relevant documents (e.g., advertisements) must be submitted to an IRB/IEC by the Investigator and reviewed and approved by the IRB/IEC before the study is initiated.

Any amendments to the protocol will require IEC/IRB approval before implementation of changes made to the study design, except for changes necessary to eliminate an immediate hazard to study patients.

Protocols and any substantial amendments to the protocol will require health authority approval prior to initiation except for changes necessary to eliminate an immediate hazard to study patients.

The Investigator will be responsible for the following:

- Providing written summaries of the status of the study to the IRB/IEC annually or more frequently in accordance with the requirements, policies, and procedures established by the IRB/EC.
- Notifying the IRB/IEC of SAE or other significant safety findings as required by IRB/IEC procedures.
- Providing oversight of the overall conduct of the study at the site and adherence to requirements of 21 CFR, ICH GCP guidelines, the IRB/IEC, and all other applicable local regulations.

Version 3.0 60 of 85 20 April 2022

10.1.2 Informed Consent Process

The Investigator or his/her representative will explain the nature of the study, including the risks and benefits, to the patient and answer all questions regarding the study.

Patients must be informed that their participation is voluntary. Patients will be required to sign a statement of informed consent that meets the requirements of 21 CFR 50, local regulations, ICH guidelines, privacy and data protection requirements, where applicable, and the IRB/IEC or study center.

The medical record must include a statement that written informed consent was obtained before the patient was enrolled in the study and the date the written consent was obtained. The authorized person obtaining the informed consent must also sign the ICF.

Patients must be re-consented to the most current version of the ICF(s) during their participation in the study.

A copy of the ICF(s) must be provided to the patient.

If a protocol amendment is required, the ICF may need to be revised to reflect the changes to the protocol. If the ICF is revised, it must be reviewed and approved by the appropriate IEC/IRB and signed by all patients subsequently enrolled in the study as well as those currently enrolled in the study.

10.1.3 Data Protection

Patients will be assigned a unique identifier by the Sponsor via the IRT system. Any patient records or datasets that are transferred to the Sponsor will contain the identifier only; patient names or any information which would make the patient identifiable will not be transferred.

The patient must be informed that their personal study-related data will be used by the Sponsor in accordance with local data protection law. The level of disclosure must also be explained to the patient who will be required to give consent for their data to be used as described in the informed consent.

The patient must be informed that their medical records may be examined by Clinical Quality Assurance auditors or other authorized personnel appointed by the Sponsor, by appropriate IRB/IEC members, and by inspectors from regulatory authorities.

Version 3.0 61 of 85 20 April 2022

10.1.4 Dissemination of Clinical Study Data

A summary of the results of the clinical study together with a summary that is understandable to a layperson will be provided after the global end (or early termination) of the study in all countries concerned to ensure full availability of all clinical data under this protocol, within 12 months.

